
## 5.0 Study Procedures

### 5.1 Study Design

This study will use an effectiveness Hybrid Type 1 design to (Aim 1) test the effectiveness of MRT in an RCT across three VA sites (Palo Alto, Little Rock, and Bedford) and (Aim 2) gather information on MRT's implementation potential in a formative evaluation.

**Aim 1:** To test the effectiveness of MRT, 365 Veterans who (a) are entering an MH RRTP, and (b) had been arrested and charged and/or released from incarceration in the past 5 years will be recruited for participation and randomly assigned to one of two conditions: usual care (UC) in the MH RRTP or MRT (condition specifics outlined below). At the beginning of the study before

participants are recruited, site PIs will generate a random number list using “randomizer.org” and create a randomization spreadsheet. Randomization will occur in blocks of six to prevent runs that might lead to unequal Ns if the full sample is not obtained. That is, we will use fixed block sizes of six to assure a roughly equal balance of subjects in the two conditions in case the study does not fully accrue. Following completion of the baseline assessment, the research assistant will add the participant to the randomization spreadsheet, notify the participant of his/her group assignment, and schedule the first MRT session for those randomized to that condition. Site PIs will review these procedures monthly with the research assistant to ensure fidelity to the process. To compare MRT to UC as UC actually exists in MH RRTPs, the number and length of project-related treatment sessions will not be equated between conditions. To reduce contamination, patients in the UC condition will not be allowed to attend MRT sessions, and the MRT group leader will remind the members at the end of each session not to discuss the group content outside of the session. Patients randomized to the UC condition will be asked not to seek out MRT during the study period of 1 year.

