## **5.2 Recruitment Methods**

**Aim 1:** We will recruit participants through MH RRTPs at each site. Veterans entering these programs will be screened by MH RRTP staff in consecutive order during the admissions process to determine study eligibility. Specifically, during the admissions process into the MH RRTP, a staff member will ask the Veteran if they were arrested and charged with a criminal offense and/or released from incarceration in the past 5 years. This is a standard question of all Veterans who enter MH RRTPs at each site. In addition, the MH RRTP staff member will verify that the Veteran is not pregnant and is conversant in English. MH RRTP staff will then ask eligible patients for permission to be contacted about the study by project staff (i.e., the MH RRTP staff member will hand the Veteran the Recruitment Sheet) and will provide study personnel with a list of these patients and their contact information (i.e., their phone number) three times per week. If the number of patients referred to the study exceeds recruitment goals, we will randomly select as many patients as needed. At each site, we will keep a list of all eligible patients whom we contacted to solicit participation in the study. Prior to contacting a potential patient, we will first verify that that patient was not already approached about participating in the study during a previous admission.

We plan to enroll approximately five patients per month at each site (approximately 1-2 patients per week). This approach aligns with standard delivery of MRT, which consists of open groups with rolling enrollment. The proposed pace will maintain appropriate group size for the MRT group facilitator and allow the research assistants to conduct assessments. 365 patients will be enrolled and complete baseline interviews. The sample will be stratified by site such that 122 patients (with rounding) will be recruited separately from Palo Alto, Little Rock, and Bedford, with 61 patients entering into each condition at each site. Regardless of group assignment, participants will also be asked to complete an in-person baseline assessment and two follow-up assessments (in-person or via phone) 6 and 12 months later. Participants will be reimbursed \$25 for the baseline interview, and \$50 after completion of each follow-up interview. Participants will have the option of being reimbursed with gift cards immediately after the completion of each interview, or receiving a check via mail in 6-8 weeks.

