### **5.3 Informed Consent Procedures**

**Aim 1:** Consent will be obtained by the site Project Coordinator, Intervention Coordinator, and/or Research Health Science Specialist who is knowledgeable about the study and trained to review the consent form with potential participants. Informed consent will be obtained in-person at one of the three VA sites (Palo Alto, Little Rock, and Bedford) prior to the start of the baseline assessment. At that time, the study will be explained in-depth and the research team member will go over all elements of the consent form with the patient. All patients will be given an opportunity to have any questions answered to their satisfaction prior to being asked to provide informed consent. Patients will be informed that they will be assigned either to “usual care” or two additional group sessions per week in the MH RRTP. The research team member will ask the potential participant questions to ensure that they understand the procedures and risks. The Research Assistants for this project (those listed in the personnel section) will be trained in Human Subjects protections and will have formally delegated responsibilities to obtain informed consent.

Prior to entry into the study, patients will be told explicitly that should study personnel learn at any time that the patient poses a danger to self or others, the researchers will need to break confidentiality, which includes making a report to the proper authorities and/or providing additional help to the patient as dictated by VA regulations and state law. Providing patients with this information is a standard and integral part of the informed consent process for research studies with Veterans and has not deterred mental health patients from participating in our studies. Further, we will use methods developed in previous and ongoing RCTs and other studies of the project team members to ensure valid and informed consent – i.e., extensive training and monitoring of project staff obtaining consent; organizing the content of the consent form into separate modules; questioning prospective participants to determine the extent of their understanding of the study purpose, procedures, and risks; encouraging the patient to ask questions regarding anything not understood.

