#### **5.4 Inclusion/Exclusion Criteria**

Veterans who (a) are entering a mental health residential rehabilitation treatment program (MH RRTP) at one of three study sites (Palo Alto, Little Rock, or Bedford VA), and (b) had been arrested and charged and/or released from incarceration in the past 5 years prior to MH RRTP admission will be eligible for participation.

The only exclusion criterion is being too cognitively impaired to understand the informed consent process and other study procedures. Patients will be screened for cognitive impairment using the Montreal Cognitive Assessment’s section on Orientation. For patients who are not able to correctly answer the Orientation (date, location) items, the research assistant will further educate the patient on the purpose of the study and procedures until he or she is able to recall and reflect on these procedures. Patients who are unable to do so will be deemed too cognitively impaired to understand the study’s procedures, participate meaningfully in MRT, and respond to interviews, and therefore will be ineligible (in our past studies of Veterans from MH RRTPs, only 1% of prospective participants was excluded on this basis). For those who are eligible, written informed consent will be obtained, and the baseline assessment will be administered.

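### Fixed blocks of six, with the size stated in the protocol, make a quarter of allocations deducible by staff who both obtain consent and announce assignments, even if the list is hidden

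*Combined protocol and SAP*

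**What the plan says.** Section 5.1 gives the randomisation method. Before recruitment "site PIs will generate a random number list using" a web tool and build a spreadsheet from it. The block size is constant and written out: "we will use fixed block sizes of six to assure a roughly equal balance of subjects". The stated reason is to keep the arms close in number if accrual falls short. After the baseline assessment, "the research assistant will add the participant to the randomization spreadsheet, notify the participant of his/her group assignment".

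Section 5.2 sets the strata: "The sample will be stratified by site such that 122 patients (with rounding) will be recruited separately from Palo Alto, Little Rock, and Bedford". The same sentence fixes the ratio at 1:1, because it ends "with 61 patients entering into each condition at each site". That the blocks run separately within each site is implied, because the site PIs make the lists, but it is not stated.

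Section 5.3 says that the research assistants "will be trained in Human Subjects protections and will have formally delegated responsibilities to obtain informed consent". It also names the Intervention Coordinator among those who take consent, and Section 6.0 describes that role as conducting the MRT groups. Section 5.5 describes only the follow-up interviewers as blinded.

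On the route into the study, Section 5.2 has programme staff screen admissions consecutively and, three times a week, "provide study personnel with a list of these patients and their contact information". No order of contact is given for the patients on that list.

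**The concern.** With a constant block size that staff know, the past reveals the future. Once one arm has used its three places, the rest of the block is fixed. The staff who enrol can know every earlier assignment at their site, because the same role announces them. At about five enrolments a month per site, a block lasts about 6/5 = 1.2 months, roughly five weeks, which is easy to follow.

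This is a separate matter from who can open the spreadsheet. It comes from the block design and would remain if every future row were locked.

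Staff who can tell which arm comes next may, without intending to, vary whom they approach, when, and how hard they pursue consent. Patients could then differ between arms in ways that randomisation was meant to prevent.

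**Working it through.** **Inputs.** Block size 6, fixed (Section 5.1). Two arms at 1:1, 61 per arm per site; three sites of about 122 (Section 5.2). 292 evaluable, 20% attrition, 365 recruited (Section 5.6).

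**The plan's own counts.** 292/0.80 = 365; 365/3 = 121.7, rounded to 122; 122/2 = 61. These reproduce. The plan states no figure for predictability.

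**Certain allocations in a 3:3 block.** There are C(6,3) = 20 equally likely arrangements.
- 4th place certain: the first three are all one arm, 2/20 = 0.10.
- 5th place certain: the last two are the same arm, 8/20 = 0.40.
- 6th place certain: always, 1.00.

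The sum is 1.5 of 6, or 25.0%. The closed form 2m/(m+1) with m = 3 gives 6/4 = 1.5.

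Per site, 122 = 20 full blocks plus 2 places, and neither leftover place can be certain. So 20 × 1.5 = 30 of 122 (24.6%) are certain. Over three sites this is 90, or 24.7% of 365.

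**Best guess.** Always guess the arm with more places left. The chance of being right at places 1 to 6 is 0.5, 0.6, 0.6, 0.7, 0.7 and 1.0. The sum is 4.1, and 4.1/6 = 68.3%, against 50% by chance.

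**Alternatives.** For random sizes, 1,500 lists of 122 were simulated with an observer who knows the possible sizes but not their order.

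| Scheme | Certain | Next arm known with probability 0.8 or more | Best guess right |
|---|---|---|---|
| Fixed 6 (exact) | 25.0% | 25.0% | 68.3% |
| Random 4/6/8 | 2.2% | 24.5% | 67.9% |
| Random 6/8/10 | 1.6% | 14.7% | 66.3% |

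Larger fixed blocks help less with certainty: 20.0% certain at size 8 and 16.7% at size 10.

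**What this means for bias.** Let staff shift a prognostic factor by δ SD towards the arm they expect.
- Acting at certain places only: bias = 2 × δ × (certain share). Fixed 6 gives 2 × 0.25 × δ = 0.50δ; random 6/8/10 gives 2 × 0.016 × δ = 0.03δ.
- Acting on every best guess, with success rate p: bias = 2 × δ × (2p − 1). Fixed 6 gives 2 × 0.367 × δ = 0.73δ; random 6/8/10 gives 2 × 0.325 × δ = 0.65δ, only 11 to 12% less.

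The benefit of varying the size therefore depends on how staff would behave.

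**Imbalance.** At 122 per site, fixed blocks leave at most 2. With sizes 6/8/10 the worst case is 4: the last block holds an even number of patients, and a block of ten can stand at 4:0 or 5:1. If accrual stops at an arbitrary point, the worst case is half the block size, 3 per site against 5.

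**The case against.** The strongest reply is that the plan leaves little room to steer and that its analysis would neutralise much of what got through.

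On the first part, Section 5.2 requires consecutive screening, random selection when referrals exceed recruitment goals, and a record of eligible patients contacted. Section 5.1 assigns after baseline and has the site PIs review the process monthly. Section 5.1 also starts MRT within a week of programme entry, so a patient cannot be held long for a later place. These points stand as limits. They do not close the gap. Consecutive order governs screening by programme staff, not contact by study staff. Random selection applies only when referrals are in excess. Assignment after baseline does not help if the next arm can already be deduced, and selective approach would leave the reviewed procedure looking intact.

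A reader might infer from the cognitive screen in Section 5.4, where "the research assistant will further educate the patient on the purpose of the study and procedures until he or she is able to recall", that staff have a discretionary exclusion to exploit. The text does not support this: the step works towards inclusion, and about 1% were excluded on this ground in past studies. Nor do the documents say how many patients are on each referral list.

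On the second part, the Section 5.6 model has a separate baseline level and slope for each arm. A stable difference in outcome level goes into the intercept and leaves the slope contrast alone. Section 5.6 also adjusts for listed baseline variables found to differ. This stands for much of any shift in measured risk. It does not reach unmeasured predictors of change: motivation is not on the list, yet it could plausibly affect completion and self-reported outcomes.

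Finally, if future rows of the spreadsheet are visible to the research assistant, block size hardly matters. That is correct, and it is why the remedy has to include concealment.

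**Conclusion.** The point holds as a design weakness that is cheap to remove. If the blocks run within site, 25% of allocations (about 90 of 365) are certain to staff who track past assignments, and 68% can be guessed correctly. One list shared across sites would make local prediction harder. Predictability is an opportunity; nothing in the documents shows that steering would occur.

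A reader might go further and infer a definite bias. For example, δ of 0.1 to 0.2 SD at every certain place gives 0.05 to 0.10 SD. That is 18% to 35% of d = 2√0.02 = 0.283 and, with SE = 2/√292 = 0.117, a two-sided type I error of 7% to 14%. The documents do not support this as an estimate. They give no value for δ. The figures also require steering in both directions at every site, and they describe an unadjusted two-group comparison, not the planned model. They are an illustration at most.

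The remaining concern is selection on unmeasured predictors of change. Its size cannot be derived from the documents.

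**What to change.** In Section 5.1, replace the fixed blocks of six with permuted blocks, stratified by site, whose size varies at random (for example 6, 8 and 10). State that each site has its own sequence. Hold the block sizes and the list in a restricted file closed to anyone who obtains consent, and leave the sizes out of the protocol text that recruiting staff use. Release each assignment one at a time, only after the baseline assessment is complete. If enrolment has begun, apply this to all remaining blocks.

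Both parts are needed: varying the size removes most of the certainty, but the best-guess rate stays near 66%, and it gives no protection if the list can be read.

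The cost is a change of wording, a different setting when the list is generated, and a person outside enrolment to hold the file. Site imbalance could reach 4 instead of 2 at 122 patients, or 5 instead of 3 if accrual stops at an arbitrary point. The plan's stated aim of rough balance under incomplete accrual is still met.

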## **5.2 Recruitment Methods**

**Aim 1:** We will recruit participants through MH RRTPs at each site. Veterans entering these programs will be screened by MH RRTP staff in consecutive order during the admissions process to determine study eligibility. Specifically, during the admissions process into the MH RRTP, a staff member will ask the Veteran if they were arrested and charged with a criminal offense and/or released from incarceration in the past 5 years. This is a standard question of all Veterans who enter MH RRTPs at each site. In addition, the MH RRTP staff member will verify that the Veteran is not pregnant and is conversant in English. MH RRTP staff will then ask eligible patients for permission to be contacted about the study by project staff (i.e., the MH RRTP staff member will hand the Veteran the Recruitment Sheet) and will provide study personnel with a list of these patients and their contact information (i.e., their phone number) three times per week. If the number of patients referred to the study exceeds recruitment goals, we will randomly select as many patients as needed. At each site, we will keep a list of all eligible patients whom we contacted to solicit participation in the study. Prior to contacting a potential patient, we will first verify that that patient was not already approached about participating in the study during a previous admission.

We plan to enroll approximately five patients per month at each site (approximately 1-2 patients per week). This approach aligns with standard delivery of MRT, which consists of open groups with rolling enrollment. The proposed pace will maintain appropriate group size for the MRT group facilitator and allow the research assistants to conduct assessments. 365 patients will be enrolled and complete baseline interviews. The sample will be stratified by site such that 122 patients (with rounding) will be recruited separately from Palo Alto, Little Rock, and Bedford, with 61 patients entering into each condition at each site. Regardless of group assignment, participants will also be asked to complete an in-person baseline assessment and two follow-up assessments (in-person or via phone) 6 and 12 months later. Participants will be reimbursed \$25 for the baseline interview, and \$50 after completion of each follow-up interview. Participants will have the option of being reimbursed with gift cards immediately after the completion of each interview, or receiving a check via mail in 6-8 weeks.

**Aim 2 (Qualitative Interviews):** We will interview six staff members at each site (the director, a nurse, a social worker, and a clinical psychologist or psychiatrist from the MH RRTP; a local VJP Specialist; and the local Mental Health Treatment Coordinator). We will also conduct interviews with 12 JIVs from each site who agreed to participate in the study and were

randomized to the MRT condition: (a) one-half will be drawn from those who completed the full dose (24 sessions) and the other half from those who dropped out and completed less than the recommended minimal dose (12 sessions). Although individuals cannot represent entire groups, we will include a diverse sample of Veterans based on age, gender, race/ethnicity, era of military service, and diagnoses (e.g., PTSD). Interviews will last 30-60 minutes; be conducted in person or via phone by Drs. [name] and [name], as well as the research assistants at each site; and audiotaped with consent. Staff interviews will take place after all patient participants have completed the intervention phase of the RCT. Specifically, within two weeks of the last MRT session for patient participants at a given site, a research staff member at the site will attend MH RRTP staff meetings and distribute the information sheet that is included in this Central IRB application. MH RRTP staff will then be informed that if they are interested in participating, they can contact the number listed at the bottom of the information sheet. Patient interviews will take place after participants have either completed or dropped out of the intervention. Specifically, within 2 weeks of completing their last MRT session, patients will be re-contacted via phone and invited to participate in the 30-60 minute interview.

### **5.3 Informed Consent Procedures**

**Aim 1:** Consent will be obtained by the site Project Coordinator, Intervention Coordinator, and/or Research Health Science Specialist who is knowledgeable about the study and trained to review the consent form with potential participants. Informed consent will be obtained in-person at one of the three VA sites (Palo Alto, Little Rock, and Bedford) prior to the start of the baseline assessment. At that time, the study will be explained in-depth and the research team member will go over all elements of the consent form with the patient. All patients will be given an opportunity to have any questions answered to their satisfaction prior to being asked to provide informed consent. Patients will be informed that they will be assigned either to “usual care” or two additional group sessions per week in the MH RRTP. The research team member will ask the potential participant questions to ensure that they understand the procedures and risks. The Research Assistants for this project (those listed in the personnel section) will be trained in Human Subjects protections and will have formally delegated responsibilities to obtain informed consent.

Prior to entry into the study, patients will be told explicitly that should study personnel learn at any time that the patient poses a danger to self or others, the researchers will need to break confidentiality, which includes making a report to the proper authorities and/or providing additional help to the patient as dictated by VA regulations and state law. Providing patients with this information is a standard and integral part of the informed consent process for research studies with Veterans and has not deterred mental health patients from participating in our studies. Further, we will use methods developed in previous and ongoing RCTs and other studies of the project team members to ensure valid and informed consent – i.e., extensive training and monitoring of project staff obtaining consent; organizing the content of the consent form into separate modules; questioning prospective participants to determine the extent of their understanding of the study purpose, procedures, and risks; encouraging the patient to ask questions regarding anything not understood.

**Aim 2:** Veterans admitted to the MH RRTPs at the project sites who agreed to participate in the study and were randomized to the MRT condition, and either (a) completed a full dose of MRT (24 sessions), or (b) dropped out and completed less than the recommended minimal dose (12 sessions), will be recruited to participate in the formative evaluation. VA staff members at each site (the director, a nurse, a social worker, and clinical psychologist or psychiatrist from the MH RRTP; a local VJP Specialist; and the local Mental Health Treatment Coordinator) will also be recruited for participation in the formative evaluation. The Veteran patients will be contacted by a member of the project team who will arrange to meet with the prospective participant to explain this portion of the project (see “Phone Script for Veterans”). Written informed consent to participate in this part of the project will already have been obtained from the Veteran patients during the informed consent procedures for Aim 1.

Verbal, rather than written, informed consent will be obtained from VA staff for Aim 2 (see Information Sheet – Waiver of Documentation of Informed Consent). Specifically, a research staff member at each site will attend MH RRTP staff meetings and distribute the aforementioned Information Sheet. MH RRTP staff will then be informed that if they are interested in participating, they can contact the number listed at the bottom of the Information Sheet. VA staff members who contact a research staff member expressing interest in participating will then be read the phone script for VA providers.

